#### 1.0 PROTOCOL SUMMARY AND/OR SCHEMA

The objective of this randomized controlled trial is to compare the effectiveness of deep ves moderate neuromuscular blockade (NMB) in reducing postoperative pain and intra-abdominal insufflation pressure in patients undergoing minimally invasive robotic prostatectomy.

Patients will be randomized into two groups: deep (intervention) versus moderate (control) NMB. In both groups, anesthesia will be induced and maintained per our department's routine and standarized as per outlined in the study design. We plan to randomize 130 patients to ensure 120 evaluable patients for each of the two primary endpoints. Enrollment of patients will be limited to Josie Robertson Surgery Center.

For each patient in either arm of the study, rocuronium infusion will not be started until there is sign of spontaneous recovery from induction dose of muscle relaxant. "Sign of spontaneous recovery" will include any twitch on Train of four (TOF) OR post tetanic stimulation. Depth of blockade will be monitored continuously with a Train-of-Four (TOF) General Electric (GE) Neuromuscular transmission (NMT) Anandic device. Rocuronium will be continuously infused and titrated according to group assignment: (i) The intervention group will have rocuronium titrated to deep paralysis defined as post tetanic count of 1-2. (ii) The control group will have rocuronium infusion titrated to moderate paralysis defined as TOF of 1-2.

All patients will be maintained in the same surgical position (angle of Trendelenburg) per robotic urological surgery standard. An initial starting intra-abdominal pressure (IAP) value will be set. All cases will begin at this value, which will be less than 10 but above 8 mm Hg. To prevent surgeon bias in initial IAP, the surgeon will be blinded to the starting IAP value. As necessary, surgeons will request an increase in pressure to improve visualization. The IAP values will be recorded at 15-minute intervals. Changes in IAP outside the 15-minute interval measurement point will also be recorded. Any request by surgeon to change IAP will be recorded independent of an actual change. The IAP value will be concealed with black tape to maintain surgeon blinding throughout the duration of the case. Increases or decreases in IAP per surgeon's request will be allowed throughout the case with scripted responses. Surgical exposure/visualization will be assessed at 30-minute intervals using the Leiden surgical rating scale of 1 to 5.

At the end of a case, patients in both arms will be reversed with sugammadex at fascia closure (i.e. all port sites are closed). Estimated blood loss will be extracted from Electronic Medical Record. Postoperatively, endpoints will be recorded on all patients by the PACU nurse and research staff according to established pain and nausea scales.. Estimated time to completion of accrual is 1 year.

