#### Intraoperative monitoring:

All patients will be monitored intraoperatively with routine monitors for oxygenation, ventilation, circulation, and temperature without deviating from standard American Society of Anesthesiologist (ASA) practice. This includes EKG, direct blood pressure, heart rate, oxygen saturation, end-tidal carbon dioxide, and temperature monitoring. Routinely, a TOF hand-held monitor is used for monitoring neuromuscular blockade. However, in this study, all enrolled patients will be monitored using a GE Anandic NMT device. The GE Anandic NMT is a FDA approved device being strictly used for this protocol on loan from GE Healthcare. The device is being used as indicated and will be utilized by a trained investigator. Members of our department have the expertise required for this device, which generates an electrical stimulus to the ulnar nerve and measures contractions of adductor pollicis muscle through a sensor attached to the tip of the thumb. A computer-generated TOF will eliminate observer variability in measuring TOF (see Appendix 8). TOF will be monitored every minute and recorded in the Electronic Medical Record. If the NMT monitor fails or cannot capture a baseline value, the patient will fall off protocol and clinician will be relegated to using a hand-held twitch monitor. However, this is an unlikely event and has not been reported during the pilot of this protocol.

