#### Standardization of Anesthetics:

General anesthesia will be induced as per department routine with minimal variation on induction and maintenance of anesthesia. Upon arrival to the operating room (OR), standard ASA monitors will be applied before induction of anesthesia. All patients will be induced with midazolam (2 mg), propofol (2 mg/kg), fentanyl (1 mcg/kg), lidocaine (1mg/kg), and rocuronium (0.45 mg/kg). This anesthetic regimen will be standardized for both the moderate (control) and deep (intervention) NMB arms.

Patients will receive 100% oxygen during induction of anesthesia. After induction, anesthesia will be maintained at an age-adjusted minimum alveolar concentration (MAC) of 1 with sevoflurane. This will be titrated to maintain a Bispectral index of 35-55. Ventilation will be maintained with tidal volumes of 7 ml/kg, FiO2 less than 50%, and positive end-expiratory pressure (PEEP) and respiratory rate aimed towards normocapnia (ETCO2 of 35-45). For all patients in both arms of the study, two antiemetics (Dexamethasone 4 mg and Ondansetron 4 mg) as well as intravenous acetaminophen (1000 mg) will be administered.

Patients with rapid sequence inductions with succinylcholine will be excluded from participation. If a rapid sequence induction is conducted with rocuronium, the patient will have to demonstrate the start of recovery  $\mathbf{q}$ 

even if the rocuronium dose exceeds 0.45mg/kg. The first sign of the start of recovery from neuromuscular blockade is defined as either the presence of a single twitch on TOF, or a post tetanic contraction of 1 or higher.

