#### 7.0 RECRUITMENT PLAN

All patients who meet all eligibility criteria and are scheduled for robotic prostatectomies performed by a surgeon listed on this protocol, will be approached to gauge interest in participating in the study.

All patients will undergo surgery at Josie Robertson Surgical Center. Potential patients will be identified by the study team ahead their scheduled preoperative visit. The study team will work closely with the urology clinic staff to ensure documents are prepared ahead of time. The consent discussion for this study will occur during the preoperative visit in the urology clinic by either the surgeon or the advanced practice provider (Nurse practitioners or physican assistants). The protocol will be described to all prospective patients by the consenting professional, who will obtain informed consent from agreeing patients. Interested patients who do not provide provide consent during their pre-operative visit will be followed up by the study team at another time prior to surgery if possible. All consent discussions will occur at least 1 day prior to the patient's surgery. There will be no compensation (financial or otherwise) to participants who enroll in the study. Accordingly, there is no direct benefit to patients who agree to participate in the study.

Surgeons involved in the study as investigators will receive a detailed fact card that will be used for their reference and to educate their patients. This fact card will include:

- 1. Background and rationale
- 2. Scientific aims
- 3. Intervention and treatment plan
- 4. Protocol summary
- 5. Contact information for PI, research study assistant

Educational program: Surgeons will receive orientation and education on all aspects of the protocol. The education sessions will first in a didactic group session one month before the start of enrollment, and followed by a one-to-one review session with the study PI one week before the start of enrollment to review details of the study.

Because of the nature of the surgical procedure, only men will be enrolled in the study. All male patients regardless of race and ethnic background will have equal opportunity to participate in the study.

To maintain uniformity in protocol execution, only the anesthesiologists and CRNAs listed as an investigator on the face sheet will be eligible to conduct the study cases.

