#### 9.0 TREATMENT/INTERVENTION PLAN

[figure not shown]
A total of 130 patients scheduled for robotic prostatectomies will be randomized into two groups: deep (experimental intervention group) versus moderate (control) blockade, with 120 expected to be evaluable for each of the two primary endpoints. In both groups, anesthesia will be induced and maintained per our department's current routine, and standardization will is clearly defined previously in the protocol. For each patient in either arm of the study, recovery from induction dose of rocuronium will be established before reinitiating muscle blockade (deep versus moderate) with rocuronium infusion. Level of the blockade will be monitored continuously with GE Anandic NMT device and dose of rocuronium will be titrated.

All patients will be maintained in the same surgical position (angle of Trendelenburg) per robotic urological surgery standard. All surgeons will be blinded to the 'starting IAP' value and the IAP value will be recorded at 15-minute intervals. Changes in IAP outside the 15-minute interval measurement point will also be recorded. Increases or decreases in IAP per surgeon's request will be allowed throughout the case. Surgical exposure/visualization will be assessed at 30-minute intervals using the Leiden surgical rating scale of 1 to 5. Surgeons will be alerted if IAP reaches 15, which is the standard upper limit of IAP at MSKCC. Investigators request they know the IAP at a level of 15, so they can weigh risk/benefit of continuing to operate at that higher threshold of IAP. At the end of a case, patients in both arms will be reversed with sugammadex at fascia closure. Data will be collected from the of the surgical case. Patients who experience unexpected intraoperative events including death, conversion to open procedure, a decline in clinical condition that would end a planned procedure, anaphylaxis, or a life-threatening hypersensitivity reaction to any medication will be removed from the study.

Estimated blood loss will be recorded from Electronic Medical Record. Postoperatively, endpoints (pain and nausea) will be recorded on all patients by a PACU nurse and research staff(up to 48 hours postoperatively) according to pain and nausea scales as described above. The a PACU nurse will perform these assessments while the patient is on-site. The research nurse will complete 24 and 48-hour assessments by telephone.

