#### 13.0 CRITERIA FOR REMOVAL FROM STUDY

Criteria for removal of subject from the study will include patient death, surgical conversion from robotic to open procedure, intraoperative deterioration in clinical condition that would end a planned procedure.

Patients are considered evaluable for the first primary endpoint (IAP) if they can provide at least one IAP recording; patients are considered evaluable for the second primary endpoint (Pain) if they can provide at least one NPS pain score within 6-hours after surgery. Study data will be analyzed according to a modified intention-to-treat principle ("modified" because patients considered inevaluable for a given primary endpoint will be excluded from the analysis of that endpoint).

The following are a list of possible perioperative scenarios. We expect these to occur extremely infrequently. We anticipate fewer than 10 occurrences during the study period and have planned the protocol accordingly.

- 1) Cancelled surgery
  - Patient will not provide either primary endpoint therefore patients in this category will be excluded from primary analysis
- 2) Patient death
  - For patients who die in the perioperative period, any data up until patient death will be analyzed. These patients may possibly contribute data for only one of the two primary endpoints (IAP)
- Surgical conversion from robotic to open procedure
   Any data up until conversion will be analyzed.

   These patients may possibly contribute data for only one of the two primary endpoints (IAP)
- 4) Intraoperative deterioration in clinical condition that would end planned procedure For patients who experience deterioration in clinical condition that ends planned procedure, any data up until deterioration will be analyzed.
  - However, there will be an investigation to assess the possible (but extraordinarily unlikely) influence of protocol in leading to deterioration.
- 5) Deviation from protocol by giving additional dose of NMB to satisfy surgeon request for better visualization
  - All data in this scenario will be analyzed.. Secondary analysis will be conducted as treated.
- 6) Equipment failure of the neuromuscular train of four monitoring device
  Any data up until failure of neuromuscular train of four monitoring device will be analyzed.patient will
  be considered evaluable for only one of the two primary endpoints (IAP).
- Accidental unblinding of surgeon
   All data will be analyzed.. This will be an evaluable patient.

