#### 15.2 Randomization

The study will be conducted in a prospective randomized fashion. We plan to randomize 130 patients in 1:1 ratio to ensure at least 120 patients would be evaluable for each of the two primary endpoints. During the registration process, research staff will complete a protocol-specific Eligibility Checklist. After consent is obtained and eligibility is established, patients will be registered as described in Section 15.1.

After successfully registering the subject, the research study staff will randomize them in CRDB (Clinical Research Database) stratified by BMI (<30 vs ≥30) and surgeon. Only the anesthesia research team (CRM and CRCs) and the anesthesia care team in the OR will have access to the arm assignments.

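### Patients are randomised at registration, before surgery, although the arms diverge only when the rocuronium infusion starts, so some pre-treatment losses become post-randomisation exclusions

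*Combined protocol and SAP*

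**What the plan says.** On numbers, Section 1.0 states: "We plan to randomize 130 patients to ensure 120 evaluable patients for each of the two primary endpoints".

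On timing, Section 15.2 has the allocation follow registration at once: "After successfully registering the subject, the research study staff will randomize them in CRDB (Clinical Research Database) stratified by BMI" and surgeon. Section 7.0 puts consent before the day of surgery: "All consent discussions will occur at least 1 day prior to the patient's surgery". Section 9.0 describes those randomised as patients awaiting an operation: "A total of 130 patients scheduled for robotic prostatectomies will be randomized into two groups".

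On what happens before the arms differ, Section 4.1 (Standardization of Anesthetics) gives one induction regimen: "This anesthetic regimen will be standardized for both the moderate (control) and deep (intervention) NMB arms". Under Maintenance and reversal in the same section, the arm-specific infusion begins only when recovery from the intubating dose first shows.

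On losses in between:
- Section 13.0, item 1, on cancelled surgery: "Patient will not provide either primary endpoint therefore patients in this category will be excluded from primary analysis".
- Section 4.1 (Intraoperative monitoring): "If the NMT monitor fails or cannot capture a baseline value, the patient will fall off protocol". Section 4.2 places the monitor's reference measurement at induction, before any relaxant.
- Section 4.1 and Section 6.2 (item 11) exclude patients who receive succinylcholine.

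Section 15.2 gives the anaesthesia care team in the operating room access to the assignments. Section 13.0 defines a modified intention-to-treat (ITT) analysis that drops patients who are not evaluable for an endpoint.

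**The concern.** An allocation made before it is needed exposes the randomised set to losses that have nothing to do with treatment. A patient whose operation is cancelled, or who leaves the protocol at induction, has received nothing that differs by arm, yet counts as randomised and then has to be removed.

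Two things are at stake. The first is the integrity of the randomised comparison. Succinylcholine use and failure to obtain an NMT baseline are settled at induction, by or in the presence of a team that can know the arm. Selection by arm is then possible, even if unintended, and the modified ITT rule offers no protection against it. The second is economy: each such patient uses up a randomisation and a slot in a BMI-by-surgeon stratum. Cancellation belongs under this second heading only.

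**Working it through.** **Step 1. Order of events.** Setting the sections side by side gives: consent (at least 1 day before surgery), registration, randomisation, possible cancellation, NMT reference measurement and induction, first sign of recovery, arm-specific infusion. Section 15.2 states no day or hour for randomisation. That it precedes surgery follows from Section 13.0: cancelled surgery can be an exclusion from the primary analysis, within an allowance that separates randomised from evaluable patients, only if such patients were already allocated.

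**Step 2. The plan's own figure.** Inputs are 130 randomised and 120 evaluable (Section 1.0).
- Allowance: 130 − 120 = 10.
- Rate: 10/130 = 7.7%.
- Check: 120/(1 − 10/130) = 130. The figure reproduces.

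**Step 3. What the allowance covers.** Section 13.0 expects fewer than 10 occurrences over all its scenarios together and gives no split.
- Clearly before the infusion: cancellation (item 1).
- Possibly after it: death, conversion, clinical deterioration (items 2 to 4).
- Mixed timing: monitor failure (item 6).
- Patient stays in the analysis: extra relaxant, accidental unblinding, monitoring issues (items 5 and 7 to 10).

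Succinylcholine induction is not on this list, so how such a patient enters the modified ITT set is left to inference.

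**Step 4. Effect of later allocation.** Let k of the 10 losses fall before the infusion. The documents do not give k, so the whole range is shown.
- Randomised for 120 evaluable = 120 + (10 − k).
- Post-randomisation exclusions = (10 − k)/(130 − k).

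| k | Randomised | Excluded after randomisation |
|---|---|---|
| 0 | 130 | 10/130 = 7.7% |
| 3 | 127 | 7/127 = 5.5% |
| 5 | 125 | 5/125 = 4.0% |
| 8 | 122 | 2/122 = 1.6% |
| 10 | 120 | 0% |

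The number consented does not move: [120 + (10 − k)] randomised + k registered only = 130.

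**Step 5. By endpoint.** One recording makes a patient evaluable for intra-abdominal pressure (IAP), and only cancellation is stated to yield neither endpoint. Patients not evaluable for IAP are therefore mostly those who never reach insufflation, and later allocation would keep most of them out of the randomised set. Losses of pain data after the arms diverge would remain.

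**Step 6. Power.** Section 14.0 gives an IAP difference of 13.9 − 11.1 = 2.8 with SD 4, a log-pain difference of 1.3 − 0.975 = 0.325 with SD 0.5, and alpha 0.025 per endpoint (taken as two-sided; the plan does not say). With n per arm, the noncentrality is difference/(SD × √(2/n)).
- n = 60: 2.8/(4 × √(2/60)) = 3.83 for IAP and 0.325/(0.5 × √(2/60)) = 3.56 for pain. Noncentral t power is 94.0% and 90.0%. Under the stated independence, at least one = 1 − (1 − 0.940)(1 − 0.900) = 99.4%.
- n = 55 (110 evaluable): 91.7% and 87.0%; at least one 98.9%.

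Ten losses more or fewer barely change the power for at least one endpoint, which the plan puts at 90%.

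**The case against.** The case for leaving the timing alone has real content.

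- **The 130 is not caused by the timing.** A reader might infer that 130 must be randomised because allocation is early. The documents do not support that: the allowance is pooled, some of it can arise after the arms diverge, and at k = 0 later allocation saves nothing. This objection stands.
- **Failed baselines may not leave the IAP analysis.** Section 13.0, item 6, keeps patients with monitor failure evaluable for IAP, and item 10 describes them as having no train-of-four measurements. Section 4.1 adds that failure is unlikely and was not seen in the pilot. This stands, and it is why a failed baseline is listed only as a possible exclusion.
- **The route to bias is narrow.** Surgeons and patients are blinded, so nothing shows how the arm could affect cancellation. The monitor sets its current and takes its reference automatically. This stands for cancellation and weakens the point for the baseline. It does not reach succinylcholine use, nor the decision to take a patient off protocol.
- **Stratum balance is a small matter.** The primary models adjust for BMI and include surgeon effects. This stands.
- **The saving is partly relabelling, and early allocation is convenient.** The same number consent either way. Allocation in the operating room adds a step during the case and a chance of unblinding the surgeon. This stands as the cost of the change and does not outweigh it.

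**Conclusion.** The point holds as a modest, inexpensive improvement in design. Allocation precedes surgery, the arms are treated alike until the infusion starts, and cancelled surgery, succinylcholine induction and possibly a failed NMT baseline can therefore become exclusions after randomisation. The last two are settled when the anaesthesia team can know the arm, which later allocation would prevent.

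The size is bounded but not known: between 120 and 130 randomised for 120 evaluable, with post-randomisation exclusions between 0% and 7.7%, depending on a split that the documents do not give. A reader might go further and conclude that the trial is underpowered or that its results will be biased. Neither follows. Power for at least one endpoint stays near 99% under the plan's own assumptions, and the documents show an opportunity for selection at induction, not evidence that it occurs.

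The conclusion assumes that randomisation is done before the patient reaches the operating room. Section 15.2 implies this but gives no hour. Allocation on the day of surgery would fit the text and would shrink the cancellation part, but not the induction part.

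**What to change.** Amend Section 15.2. Register and confirm eligibility before surgery as now, but obtain the allocation from the Clinical Research Database, with the same BMI and surgeon strata, in the operating room after induction and a valid NMT reference measurement and before the infusion starts, out of the surgeon's sight. Cancelled cases, succinylcholine inductions and failed baselines are then registered but never randomised. Exclusions under Section 13.0 then concern only events after allocation.

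The cost is protocol wording and one electronic look-up per case. Allocation is already electronic, and researchers already photograph electrode placement in the operating room (Section 16.0). The downside is that the allocation must be available promptly, because the infusion is tied to the first sign of recovery, and the look-up must be concealed from the surgeon.

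If accrual is too far advanced to change the timing, report every exclusion before the infusion by arm, with its reason and whether it was decided with the arm known.

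In either case, reconcile Section 4.1, which takes a patient off protocol when the monitor fails, with Section 13.0, item 6, which keeps that patient evaluable for IAP. State also how a patient given succinylcholine after randomisation is handled in the modified ITT set.
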